4. STUDY DESIGN

4.1. Overall Design

This study is a multi-site, open-label case series collecting data on the clinical use of an esterified hyaluronic acid wound matrix in preparing post-escharectomy wounds in burn patients for STSGs. The study will be split into two phases. Phase I will include use of the device on the wound, with the intent of measuring how quickly the wound becomes prepared for an STSG. Phase II will occur after the STSG is placed; in this phase, the device will not be applied. Rather, the key assessment will be how well the wound is receiving the STSG. The Schedule of Activities in Section 1.2 describes the timing and sequencing of the events and phases.

In addition to the use of the wound device, physicians will provide the standard of care per their facility. However, in order to avoid confounding any conclusions attributable to the wound matrix, negative pressure wound therapy (NPWT) of the target wound will not occur during the study. Patients having NPWT on the target wound when they are screened may be included in the study (provided they meet all the inclusion criteria and none of the exclusion criteria), except when NPWT is not or cannot be discontinued after application of the device. The potential use of NPWT on the target wound, after application of the device, on a patient is listed below as an exclusion criterion. During the course of the study, if a physician determines that a patient could benefit from NPWT on the target wound, the physician can implement this therapy, and the patient will be discontinued from the study.

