6.1.2.5. Infection Evaluation

At this visit, as well as all visits and during the continuum of the patient's participation in the study, the wound site will be evaluated for the development of an infection. In the event of a suspected infection, clinical staff will collect a wound culture. Should a patient develop an infection, this will be noted as an expected adverse event (AE) and the participant's participation in the study will be terminated.

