At the interim visits during Phase I, patients will have their wound assessed, and will then be photographed using the same method as described in section 6.1.2.2. Remaining Interim visit activities will then be performed as stated in 6.1.2.3 through 6.1.2.5. The site investigator will assess if the wound is ready to receive an STSG at these visits. If the wound is ready for an STSG, the date of STSG approval and planned date of STSG procedure will be noted on the CRF provided by Medline Industries, Inc.. Should the site investigator deem that healing has progressed such that an STSG is no longer necessary, the patient's participation in the study will be discontinued. If after 21 days of device usage the patient is not ready to receive an STSG, a second application of the device may be applied and Phase I will be extended for an additional 21 days (for a maximum of 42 total days of device usage). If the patient is unwilling or clinically inappropriate, per determination by the PI, to receive a second application of wound matrix or STSG after 21 days, the patient's participation in the study will end. Alternatively, if the site investigator believes the wound will be ready to receive an STSG within three additional days of healing, but does not require another device application, the silicone backing of the device will be removed at Day 21 and the STSG will be scheduled by the Investigator or treating physician. Similarly, after 21 days of second application of the device, if the site investigator believes the wound will be ready to receive an STSG within three additional days of healing, the silicone backing of the device will be removed 21 days after the second application of the device and the STSG will be scheduled by the investigator or treating physician. STSG will be scheduled by the investigator or treating physician. Information pertaining to length-of-stay and discharge will also be collected. The timing of the visit days is approximate, as scheduling challenges may cause the exact visit days to not occur exactly every seven days. However, visits should occur within +/- two days of the original sevenday interval.

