6.2. Phase II – Post-STSG

6.2.1. Interim Visits – Post-STSG Days 7, 14, 21, 28,

Following the completion of the STSG procedure, the patient will attend up to four interim visits to monitor wound healing progress and percent take of the STSG. Also, at Day 7 visit, information relating to the graft procedure will be recorded on the Surgical Procedures CRF provided separately by Medline Industries, Inc. At each visit, a photograph of the wound will be taken and the site investigator will also determine the percentage of STSG take at each visit, which will be based on the clinical judgement. The patient will also rate current pain level (overall and at the target wound) in an identical fashion to Section 6.1.2.3. A patient's participation in Phase II of the study will continue for 28 days post-STSG or until the site investigator determines weekly care is no longer needed. To document wound healing completion, a photograph of the healed wound will be taken. In order to track the participant's overall outcomes, any returns to the operation

A clinical evaluation of an esterified hyaluronic acid matrix on preparing wounds in burn patients for split-thickness skin grafting

MED-2018-DIV31-006

V2.0

CONFIDENTIAL

room to treat the target wound, any additional inpatient stays, and the type of facility the patient goes to at discharge will be captured on the CRFs. The timing of the visit days is approximate, as scheduling challenges may cause the exact visit days to not occur exactly every seven days. However, visits should occur within +/- two days of the original seven-day interval.

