8. STATISTICAL CONSIDERATIONS

8.1. Sample Size Determination

This study is a case series meant to evaluate the clinical usage of the device and is not intended to inform any hypothesis testing. Therefore, a sample size of 20 patients was chosen, which is consistent with a case-series.

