8.2. Populations for Analyses

An evaluable population will be used for all analyses, with the definition of evaluable depending on the Phase of the study. For Phase I, all patients with an initial visit and a final interim visit resulting in resolution of Phase I will be included. In Phase II, patients with data from any interim visits who also complete Phase II to resolution will be included in analyses for Phase II.

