8.3. Statistical Analysis

Descriptive statistics, including measures of central tendency (mean or median), measures of variation (standard deviations, coefficients of variation) and 95% confidence intervals and interquartile ranges, as appropriate, for the data distribution will be calculated for all endpoints. Demographic and baseline characteristics will be assessed as above and additional statistical analyses may be conducted in an exploratory fashion, as appropriate, for the data distribution.

- Time (in days) from initial application of wound matrix to approval of wound to receive an STSG.
- Change in wound volume from the time prior to application of the wound matrix to the time before the application of STSG and after STSG
- Length-of-stay as an inpatient

A clinical evaluation of an esterified hyaluronic acid matrix on preparing wounds in burn patients for split-thickness skin grafting

MED-2018-DIV31-006

V2.0

CONFIDENTIAL

- Patient pain ratings
- Proportion of STSG take, per clinician judgement, for the wound at 28 days
- Proportion of patients who develop an infection of the target wound at any time, per confirmation with culture
- Type of care setting where patient is discharged

Healthcare economics outcomes will be explored by combining length-of-stay data (both phases) and the type of care setting where the participant is discharged, with standard costs, reimbursement codes and other relevant health economics economic factors.

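### Infection endpoint 1e, reported alone, cannot separate infection before grafting from infection after it, and Section 8.2 gives it no workable denominator

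*Combined protocol and SAP*

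**What the plan says.** Section 8.3 lists among its descriptive summaries the "Proportion of patients who develop an infection of the target wound at any time, per confirmation with culture". The synopsis and the Section 3 table word the endpoint the same way. None of the three places splits it by phase or names a denominator, and no time-to-infection analysis is planned.

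Participation covers two periods. In Phase I the device is on the wound, "for a maximum of 42 total days of device usage" (Section 6.1.3). Section 4.1 then states: "Phase II will occur after the STSG is placed; in this phase, the device will not be applied". Phase II follow-up is to "continue for 28 days post-STSG or until the site investigator determines weekly care is no longer needed" (Section 6.2.1).

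Section 6.1.2.5 says that at all visits and "during the continuum of the patient's participation in the study, the wound site will be evaluated for the development of an infection". It also says that a patient who develops an infection is terminated from the study. Section 4.2 and the synopsis entry on participant duration agree.

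On populations, Section 8.2 says: "An evaluable population will be used for all analyses, with the definition of evaluable depending on the Phase of the study". The Phase I set needs a final interim visit that resolves Phase I. The Phase II set needs completion of Phase II to resolution. Endpoint 1e is assigned to neither.

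Section 8.1 says that "a sample size of 20 patients was chosen, which is consistent with a case-series" and that the study "is not intended to inform any hypothesis testing".

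**The concern.** The two phases differ in what is on the wound and in who is at risk. Every treated patient can have an infection before grafting. Only grafted patients can have one afterwards, and a patient infected in Phase I never reaches Phase II. A single proportion therefore combines two risks with different sets at risk, and it shifts with the share of patients grafted even if neither risk changes.

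The denominator matters at least as much. The synopsis description of the intervention lists three ways in which Phase I ends: the wound becomes ready for a graft, a graft becomes unnecessary, or two applications pass without approval. Infection is not among them; it appears only as a reason for participation to end. A patient withdrawn for infection may thus be said not to have resolved the phase and be left out of the evaluable set. An infection rate calculated after removing infected patients would be meaningless.

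Because the study is descriptive, its summaries are its whole product. A reader of 1e should be able to see who was counted and at which stage the infections occurred.

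**Working it through.** **Plan's own figure.** There is nothing to reproduce. The 20 patients of Section 8.1 were chosen by convention, and the documents state no infection rate, target precision or number expected to be grafted. The counts below are assumptions for illustration.

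**Identity.** Infection ends participation, so each patient has at most one event. Let N be the number treated, x1 the infections before grafting, n2 the number grafted and x2 the infections after grafting. Write p1 = x1/N, g = n2/N and p2 = x2/n2. With all treated patients in the denominator,

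any-time proportion = (x1 + x2)/N = p1 + g × p2.

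Check with x1 = 2, n2 = 18, x2 = 2: 2/20 + (18/20) × (2/18) = 0.10 + 0.10 = 0.20.

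**What one pooled figure allows.** Take 4 infections among 20 treated: 4/20 = 20.0%. The number grafted is 20 minus x1 minus any others who leave Phase I ungrafted. Limits are exact 95% (Clopper-Pearson): the 0.025 quantile of Beta(x, n − x + 1) and the 0.975 quantile of Beta(x + 1, n − x), with the lower limit 0 when x = 0.

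| Others leaving ungrafted | Before graft | Grafted | After graft |
|---|---|---|---|
| 0 | 0/20 = 0% (0 to 16.8) | 20 | 4/20 = 20.0% (5.7 to 43.7) |
| 0 | 2/20 = 10.0% (1.2 to 31.7) | 18 | 2/18 = 11.1% (1.4 to 34.7) |
| 0 | 4/20 = 20.0% (5.7 to 43.7) | 16 | 0/16 = 0% (0 to 20.6) |
| 4 | 0/20 = 0% (0 to 16.8) | 16 | 4/16 = 25.0% (7.3 to 52.4) |
| 4 | 2/20 = 10.0% (1.2 to 31.7) | 14 | 2/14 = 14.3% (1.8 to 42.8) |
| 4 | 4/20 = 20.0% (5.7 to 43.7) | 12 | 0/12 = 0% (0 to 26.5) |

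Every row gives the same pooled 20.0% (5.7 to 43.7). The pre-graft risk runs from 0% to 20% and the post-graft risk from 0% to 25%. With 2 infections in 20 (10.0%), the same calculation gives 0% to 10% and 0% to 12.5%.

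**Direction.** Over all treated patients, the pooled figure is never below the pre-graft risk. It is below the post-graft risk only when p1 < (1 − g) × p2. In the fourth row, 0 < 0.2 × 0.25 = 0.05, so 20% understates 25%. In the fifth row, 0.10 exceeds 0.3 × 0.143 = 0.043, so 20% overstates 14.3%.

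**Denominator under Section 8.2.** Keep 4 infections in 20 and suppose nobody else leaves ungrafted.

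- Phase II set read strictly: 20 − 4 = 16 patients complete the phase, none of them infected. Result 0/16 = 0% (0 to 20.6), whatever the split.
- Phase I set read strictly, counting infections at any time: x2/(20 − x1). This is 4/20 = 20% if all four follow grafting, 2/18 = 11.1% for a two-two split, and 0/16 = 0% if all four precede it.
- Resolution read as any ending, with all treated patients kept: 4/20 = 20%.

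The wording allows all three.

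**Ascertainment.** Section 6.1.2.5 puts infection evaluation at all visits. The Section 1.2 schedule marks the row containing it for Day 1 and the Phase I visits, not for Phase II, and Section 6.2.1 does not list it among Phase II activities. Adverse event assessment may still pick up infections after grafting, since Section 7.1 counts infection as an adverse event. Even so, the passages differ on whether infection is actively looked for after grafting.

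**The case against.** The strongest reply is that 1e does what it sets out to do. It is a secondary endpoint, and the secondary objective in the synopsis concerns outcomes of both the wound and the graft. An any-time proportion answers that. This stands: the endpoint is neither an arithmetic error nor a contradiction, and it should be kept.

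A second reply is that little is lost. Infections are recorded as adverse events, each patient has at most one to place before or after grafting, and Section 8.3 permits exploratory analyses. The split could probably be made later. That lowers the cost of the gap without closing it, because permission is not a commitment and Section 8.2 still leaves the denominator open.

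A third is that 20 patients cannot distinguish the phases. The intervals above do overlap heavily. The purpose of the split is to show where the infections fell, not to compare phases.

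A reader might go further and infer that pre-graft infections measure harm from the device and post-graft infections measure harm from surgery. The documents do not support that. There is no comparator, and relatedness is judged case by case under Section 7.4. The instructions for use allow unresorbed matrix fibres to stay in the wound, so a grafted wound is not necessarily free of device material. Nor do the documents support a general claim that pooling hides a high post-graft rate: the direction depends on the split and on the share grafted.

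**Conclusion.** The point holds in a limited form. Endpoint 1e is a valid whole-course summary, but reported alone it identifies neither the pre-graft nor the post-graft risk, and Section 8.2 gives it no usable denominator. With four assumed infections in 20 and up to four other patients ungrafted, one pooled 20% is compatible with 0% to 20% before grafting and 0% to 25% after. The same data could appear as 0/16 under strict evaluability.

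The identity and the ranges rest on infection ending participation, which the protocol states, and on all treated patients forming the denominator, which it does not. The 0/16 result also requires that withdrawal for infection is not treated as resolution. A reader might infer that infected patients will certainly be dropped; the text leaves this open and does not require it. The counts are illustrative. This is a worthwhile clarification to a descriptive analysis and does not undermine the study.

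**What to change.** In Sections 8.2 and 8.3, report culture-confirmed infection of the target wound on three lines:

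1. at any time during participation, over all patients who received the device;
2. from first application to grafting, over all patients who received the device;
3. from grafting to the end of Phase II, over all grafted patients.

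Give exact (Clopper-Pearson) 95% limits for each. State that patients whose participation ended because of such an infection count as events, and that these lines do not use the evaluable sets of Section 8.2. Add that the split is descriptive and assigns no cause.

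Reconcile the Section 1.2 schedule with Section 6.1.2.5 on infection evaluation in Phase II, since line 3 depends on it. Confirm that the case report form records the actual graft date. Section 6.1.3 mentions the approval date and planned date, and graft information is collected at the Day 7 visit after grafting, so check that the date is also captured for a patient withdrawn before that visit.

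The cost is a short change to two sections, the schedule reconciliation and a check of the form. If the passages are reconciled as Section 6.1.2.5 reads, no new assessment is needed. The price in the results is wide phase-specific intervals: for example, 2/18 gives 1.4% to 34.7%.

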9. SUPPORTING DOCUMENTATION AND OPERATIONAL CONSIDERATIONS

9.1. Clinical Monitoring

The Clinical Research Associate (CRA) will confirm that the rights and well-being of subjects are protected, and that the reported trial data are accurate, complete, and verifiable from source documents. Moreover, the CRA will confirm the conduct of the trial by the site investigators and sites are in compliance with the protocol, GCP, and regulatory requirements as well as any applicable institution or IRB and federal or local processes. Monitoring will occur at minimum every two months, or more or less depending on enrollment, during the study duration or more frequently if:

- The volume or quantity of data is large or there is a backlog of review due to unexpected issues
- This would also include any large volume of CRFs to be reviewed
- The site compliance with the protocol or compliance with expected ICH/GCP and regulatory requirements is lacking or there are continuing unresolved compliance issues
- There are unexpected AE/SAE or subject safety concerns noted
- There are any unexpected inconsistencies with study product management
- There is a request for more frequent monitoring by the site
- Any mutually agreeable situation as determined by the sites and Medline

The frequency of routine monitoring may be increased to a longer interval after three monitoring cycles if on-site situations support this change. CRA will discuss this with Medline Director or Clinical Managers and will inform the site investigator prior to implementation.

Monitoring activities will include subject eligibility, source data review, CRF completion verification, product accountability, site continued suitability, investigator study oversight, compliance, and all general monitoring activities as outlined in FDAs Code of Federal Regulations and ICH/GCP guidelines that guide that activity.

Medline Industries Inc. may, on occasion, contract with external Clinical Research Organizations to provide CRA services and those CRAs are authorized to act on behalf of Medline Industries, Inc.

A clinical evaluation of an esterified hyaluronic acid matrix on preparing wounds in burn patients for split-thickness skin grafting

MED-2018-DIV31-006

V2.0

CONFIDENTIAL

It is expected that the site will be compliant with any institutional Standard Operating Procedures during the execution of the protocol and evidence of that compliance should be readily documented and verifiable by the CRA.

The CRA will generate an internal Medline Industries Inc. visit report that will be filed with the Medline Industries, Inc. trial master file and will provide the site investigators a detailed follow-up letter after each monitoring visit that will outline the completed monitoring activities as well as any identified areas of concern and the expected/applicable corrections needed. Medline Industries Inc., reserves the right to perform audit of the study activities – either routine or for-cause – as needed, and may also perform clinical monitoring audit as well.

9.2. Regulatory and Ethical Considerations

9.2.1. Confidentiality and Privacy

Participant confidentiality and privacy is strictly held in trust by the site investigators, their staffs, and the Sponsor. Therefore, documentation, data, and all other information generated will be held in strict confidence. No information concerning the study or the data will be released to any unauthorized third party without prior written approval of the Sponsor. All study data and study records will be managed and stored in accordance with the site's HIPAA compliant policies on data storage and security. All electronic transmission of data will adhere to HIPAA Security Rules.

The study monitor, other authorized representatives of the Sponsor, representatives of the IRB and regulatory agencies may inspect all documents and records required to be maintained by the site investigators, including but not limited to, medical records (office, clinic, or hospital) and pharmacy records for the participants in this study. The clinical study sites will permit access to such records.

A master list linking subject numbers to patient name and medical record number will be maintained in a secure database or secure paper file(s) by the site investigators. The study participant's contact information will be securely stored at each clinical site for internal use during the study. At the end of the study, all records will continue to be kept in a secure location for at least a period of two years, or longer if dictated by the reviewing IRB, Institutional policies, Sponsor requirements, or ICH/GCP and FDA requirements. The site investigator will agree to notify Sponsor of any intent to move or destroy these documents.

Study participant research data, which is for purposes of statistical analysis and scientific reporting, will be maintained at the research sites on the CRFs. Copies of the CRFs, which will not contain any identifiable information, will be provided to the Sponsor for the purposes of data analysis. The study data entry and study management systems used by clinical sites and by Medline Industries, Inc. research staff will be secured and stored in an access controlled locked drawer (any paper forms) and password protected (electronic records). At the end of the study,

A clinical evaluation of an esterified hyaluronic acid matrix on preparing wounds in burn patients for split-thickness skin grafting

MED-2018-DIV31-006

V2.0

CONFIDENTIAL

all study databases that are not already de-identified will be de-identified and archived at Medline Industries, Inc.

9.2.2. Safety Oversight

Given that this is a post-market study on a device used in accordance with its labeling, there is minimal safety risk to participants. The site investigators specialize in treating burn wounds and are qualified to provide adequate safety oversight for the study. In the event there are any AEs or SAEs, the site investigator will review them and make any necessary safety determinations as needed.

